6.1.3 Other Methods

No other methods are used.

6.2 Procedure for unblinding (code break)

There is no provision for the statistician to be blinded.

6.3 Procedure for unblinding (code break)

Blinding the investigators and/or study participants is only permitted if an unforeseen incident or medical problems occur during or after the completion of study participation in a subject, which may be attributable to participation in the study.

In the event of incidents (AEs) that occur during or shortly after thermal application (within the first 24 hours) and can potentially be attributed to the application of the topical product, the principal investigator may, at his or her discretion, immediately waive the blinding of the study participant and the investigators present in order to ensure adequate treatment of the study participant.

In the case of incidents (AE) that occur more than 24 hours after the application of the topical product, clarification with a physician is mandatory and a medical certificate is required for the removal of blindness. Data may then also be passed on to the attending physician with the consent of the study

SUPSI

participant concerned. This approach is justified because with the topical products used here, no life-threatening incidents are to be expected after the intervention due to these applications.

SUPSI

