5.3 Security considerations

No further results are recorded that would serve safety.

Discontinuation of the experiment is the responsibility of the examiner with regard to the subject's subjective feelings and expressions.

If a test subject does not feel well during the application according to his or her subjective assessments, he or she can discontinue the experiment and withdraw participation in the study without any disadvantages. Distilled water and wipes are available within easy reach to wipe the product, as well as cold packs to alleviate possible skin irritation.

SUPSI

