9 STUDY STRUCTURE & EVALUATION

9.1 Schedule Study Protocol

1. **Contact by e-mail, then by phone by the director of studies**
 - a. Rough explanation of the study
 - b. Announcement of the inclusion and exclusion criteria, corresponding examination of the suitability of the test persons
 - c. If interested and suitable, delivery of further documents (see point 2)
2. **Subject information, declaration of consent**
 - a. Clarify possible questions
 - b. If the subject agrees, make an appointment for screening tests
3. **On-site explanations plus screening tests (pregnancy test (for women only), skin discrimination test, product skin compatibility), 1st day of contact**
 - a. Time required 30min
 - b. If the test person is suitable and consented, sign the declaration of consent and make an appointment for the actual measurement
4. **Measurement day on site, 2nd contact day**
 - a. 30min (cleansing of the skin in the application area and 20-minute room acclimatization, marking of the application area and adjustment of the measuring equipment)
 - b. Executing the test protocol (see Intervention)

Intervention

- Baseline measurement:	1min
- Application of topical product:	1min
- Follow-up measurement time 0min:	1min
- Follow-up measurement time 10min:	1min
- Follow-up measurement time 20min:	1min
- Follow-up measurement time 30min:	1min
- Follow-up measurement time 40min:	1min
- Follow-up measurement time 50min:	1min
- Follow-up measurement time 60min:	1min

Total Time Expenditure Intervention: approx. 100 min

The total time required for both contact days together results in a duration of 130 minutes per test subject.

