9.1.5 Collection of safety parameters

Apart from the health questionnaire (including pregnancy test for female subjects), the ability to discriminate against the skin and a skin compatibility test (product application in a small area on the volar forearm), no safety parameters are collected.

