2.4 Conclusion and compensation

After the last follow-up measurement at 60 minutes, the experiment is over for the test subject. He/she will receive the amount due to him/her according to the advertisement.

The lump sum is 50.-CHF.

SUPSI

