10.3.1 Definition and recording of safety-relevant events

An adverse event (ADVERSE EVENT) AE) is any unfortunate medical occurrence in a study subject who is exposed to a single application of a topical product (as listed in Chapter 8.1.1) that is not necessarily causally related to the study process. An AE can therefore be any adverse and unintended sign, symptom, or temporal illness with the use of an intervention product (according to Chapter 8.1.1), either or in relation to the medical intervention product (according to Chapter 8.1.1). The package leaflets

SUPSI

of the products used here describe possible side effects. These include skin itching, redness, burning as occasional side effects, eczematous skin lesions as rare and pronounced hypersensitivity reactions as very rare side effects.

According to swissethics.ch, a serious adverse event (SAE) is classified as any unfortunate medical occurrence that results in death, is life-threatening, requires or prolongs hospitalization of the subject, results in a persistent or significant disability/inability, or is a congenital anomaly/birth defect. In our study, SAE is not expected due to the possible side effects described in the product package inserts and/or product patient information.

The topical products used in this study are applied according to their package leaflet (not on mucous membranes, open, bleeding wounds / not near the eyes / not in case of hypersensitivity to one ingredient / not in subjects with bronchial asthma / not in subjects with renal insufficiency / not in children, pregnant women, during breastfeeding / do not cover with bandage or compress / do not cover several preparations at the same time on the same skin area). The contraindications and precautions described in the respective package leaflets are taken into account in the health questionnaire and the screening test. Thus, possible vulnerable subjects are recorded before the actual product application and excluded from the study. In addition, the one-time product application is below the recommended dosage according to the package inserts (massage briefly several times a day (max. five times) in a thin layer without pressure / rub in a sufficient amount on desired parts of the body).

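### Section 6.3 foresees product-related events more than 24 hours after application, but scheduled contact ends at 60 minutes and no step asks about later events

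*Combined protocol and SAP*

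**What the plan says.** All references are to the combined protocol and SAP.

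- **Late events are foreseen.** Section 6.3 allows unblinding for problems "during or after the completion of study participation in a subject" that may be attributable to the study. It sets one condition for events in the first 24 hours (discretion of the principal investigator). For "incidents (AE) that occur more than 24 hours after the application of the topical product" it sets another (physician clarification and a medical certificate).
- **The event definition is open-ended.** Section 10.3.1 defines an adverse event without a time limit. From the package leaflets it lists itching, redness and burning as occasional, and "eczematous skin lesions as rare and pronounced hypersensitivity reactions as very rare side effects". It gives no onset times.
- **Contact stops at one hour.** Section 9.2.2, item 2.4: "After the last follow-up measurement at 60 minutes, the experiment is over for the test subject". Section 9.1: "The total time required for both contact days together results in a duration of 130 minutes per test subject".
- **No later safety collection.** Section 5.3: "No further results are recorded that would serve safety". Section 9.1.5 says that, apart from the health questionnaire, pregnancy test, skin discrimination test and forearm compatibility test, "no safety parameters are collected". Section 11.4.5 plans no safety analysis.
- **Session incidents are covered.** Section 9.1.5.1 stops the experiment for an allergic reaction. Sections 9.1.6 and 10.3.1 list what is recorded about an incident, and 10.3.3 requires immediate internal reporting, prompt notice to the ethics committee, and a report on protective measures within two days.
- **Long-term view.** Section 4.4 expects no long-term risks.

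**The concern.** The plan writes rules for events that come to light after the participant has left, but describes no step by which the team would learn of them. The duties in 10.3.3, and the option in 2.9 to stop the study for safety, begin only once an event is known. Participants are treated one after another with products from the same list. If a reaction appears after release and the participant does not report it, further participants may receive the same product before anyone can act. Participant safety is at stake here; no outcome estimate or test in section 11 is affected.

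**Working it through.** **Step 1. Does the stated contact time leave room for a later contact?**

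Inputs from 9.1: first contact day 30 min; measurement day about 100 min; stated total 130 min.

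- 30 + 100 = 130 min, which reproduces the stated total.
- Built from its parts, the measurement day is 30 (preparation) + 1 (baseline) + 1 (application) + 60 (follow-up) + 1 (last measurement) = 93 min, consistent with about 100.

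The two contact days use the whole budget. Sections 9.1 and 9.2.2 list no later call, visit, diary or questionnaire.

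**Step 2. Does another section supply the missing step?**

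- The subsections on follow-up of adverse events (10.1.3 and 10.2.3) contain only a dash. Section 10.3, the category A section that applies, has no such subsection.
- Section 10.3.1 ends participation for anyone with a listed side effect and describes no later contact with that person.
- The forearm compatibility test is read for 10 minutes (Synopsis, Preparation). No check of the forearm on the second contact day is specified, and the test does not cover the 3 g application.
- Sections 9.1.6, 10.3.1 and 10.3.3 say what happens to an event once it is known. They do not say how one arising after release becomes known.

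**Step 3. What could active follow-up show?**

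If n participants are actively followed and none reports an event, the one-sided 95% upper limit for the event probability is 1 − 0.05^(1/n).

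- n = 105 (all planned, pooled over products): 1 − 0.05^(1/105) = 2.8%.
- n = 15: 1 − 0.05^(1/15) = 18.1%. The documents give 15 only for the sub-analysis product. For any other product it would be an assumption, because numbers per product are not stated and 8.1.1 lists eight products.

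**Step 4. Whom can a change still reach?**

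Table 1 places warming-product data collection in 2017 and cooling-product collection from March 2019. Version 04 is dated 24.06.2019, and the sub-analysis is scheduled for September to October 2019. On that schedule the change reaches the 15 sub-analysis participants plus those of the 45 cooling participants not yet treated. That number is not given, so the range is 15 to 15 + 45 = 60:

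- n = 15: 18.1%.
- n = 60: 1 − 0.05^(1/60) = 4.9%.

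The 2.8% figure therefore describes a study followed actively from the start and is no longer attainable if Table 1 was kept. Without active follow-up, an absence of reports supports no such limit for late events.

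**The case against.** Section 6.3 is an unblinding procedure. It says what may be done if an event comes to light and does not define a period over which data must be collected, so a session ending at 60 minutes does not contradict it. That stands: a reader might infer that 6.3 creates an observation window which the schedule fails to fill, and the text does not say so. It shows only that the plan expects such events could reach the team.

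A reader might also infer that the eczematous and hypersensitivity reactions in 10.3.1 are delayed reactions that the plan ignores. The section classifies them by frequency and gives no onset times, so that reading is unsupported.

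Nor does the plan collect nothing after screening. Incidents are recorded and reported, and erythema, temperature, perfusion and thermal comfort are measured up to 60 minutes. A separate skin inspection before release would largely duplicate these.

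Finally, passive reporting can be defended in a category A study of over-the-counter products, with a single application stated to be below the package-insert dosage, prior screening, and no safety objective. The participant information is an appendix that was not available and may ask participants to report late reactions. These points limit the weight of the concern. They do not remove it: self-report is still passive, and neither 9.1 nor 9.2.2 describes a route for it.

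**Conclusion.** The concern holds as a gap in how late events become known. The plan foresees attributable events after participation, including beyond 24 hours, while scheduled contact ends at 60 minutes and no later question is asked. A late event is then learned of only if volunteered, and 10.3.3 may not be triggered before others receive the product.

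This is a cheap improvement to participant safety and not a defect in the analysis. The plan makes no tolerability claim, so none is invalidated; if one were made later, it could rest only on the session and on volunteered reports.

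The conclusion assumes that the unavailable participant information schedules no contact. The frequency of late reactions is unknown from these documents, so no number of missed events can be given.

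**What to change.** - Add to 9.2.2, item 2.4, one scripted e-mail or phone contact after the 24-hour mark used in 6.3, at a time the sponsor sets. Apply it to all participants still to be treated, including those who stop early.
- Ask yes/no about each side effect listed in 10.3.1 and record the answers on the existing incident sheet named there. Record non-response as such, not as no event.
- Amend 5.3 and 9.1.5 to match, and reconcile 4.4, 5.3, 6.3, 9.1.5, 9.2.2 (item 2.4) and 10.3.1 to 10.3.3 so that they describe one route for late events.
- State that these safety records are kept whatever is decided on early stoppers' data, where 7.4 and 9.1.6 (evaluate and include) conflict with 8.5 and 11.5 (destroy).
- If a limit is quoted, use the number actually followed, by product where the question is about a product.

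Cost: protocol and information-sheet wording, and a few minutes per participant for the study director, who already contacts participants by e-mail and phone (9.1). Some will not reply. No extra visit or staff is needed. How any reaction is managed is for the sponsor to settle.

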7 STUDENT POPULATION

7.1 Inclusion Criteria

Inclusion Criteria

- Adults aged 18 to 40 years
- No surgical interventions on the musculoskeletal apparatus in the area of the trunk
- Injuries to the trunk that occurred more than a year ago and do not cause any symptoms (pain at rest or during exertion, swelling, redness, restriction of movement of the adjacent joints)
- Closed skin and scar conditions

Exclusion criteria

- Age over 40 years
- Surgical interventions on the musculoskeletal apparatus in the area of the trunk
- Current injuries of any kind (skin abrasions, burns, sprains, muscle or tendon strains, bruises, fractures) in the area of the trunk that are still symptomatic
- Injuries to the trunk that were not more than a year ago and/or still cause symptoms
- Scars in the lumbar back area
- Fear of application
- Regular intake of medication (including self-purchased medication), with the exception of contraception drugs
- Metal implants in the area of the trunk (neck C7 to pelvis, sacrum and hip joints)
- Known allergies to the ingredients of the topical application (wintergreen oil, menthol, alcohol)
- Lack of skin discrimination capacity lumbar epicritically and protopathic (pointed-blunt, warm-cold, sense of vibration)
- Renal failure
- Bronchial asthma
- Pregnancy / breastfeeding
- Diabetes mellitus type 1 or 2
- Polyneuropathies

7.2 Recruitment and Screening

SUPSI

Recruitment

It is advertised on the website (homepage & Facebook) of the "Thim van der Laan" University College Physiotherapy. In addition, information posters will be hung up in the school building. The exact texts have been prepared according to the checklist of the Cantonal Ethics Commission Zurich.

As advertisements (text visible):

- Homepage of the Thim van der Laan Physio School: www.physioschule.ch
- Facebook page of the Thim van der Laan School of Physiotherapy: <https://www.facebook.com/physioschule>

Screening

During the first contact, the potential participants are informed about the course and risks of the study, as well as the conditions for and the amount of compensation explained. A checklist for contacting them by telephone serves as a basis.

During the first telephone contact, a questionnaire is filled out by the study management to determine the suitability as a study participant.

Advertisements and health questionnaires for the first contact can be found in the supplement.

7.3 Group assignment

The group allocation (warming product, cooling product) is concealed by means of a lot in a sealed envelope, which is drawn under the supervision of the study leader. The product to be applied and the side of the application area are noted on this lot. The examiner determines the examination condition and only passes on the subject number to the assessor. At the end of the entire data collection, the auditor pools the data sets according to the application.

7.4 Discontinuation of study participation

If a participant withdraws from the study, the lot of the allocation is returned to the pot in a new envelope and a new participant is sought.

All data collected to date will be evaluated as far as possible and included in the data analysis (in accordance with Art. 9 ClinO). After evaluation, the data is irreversibly anonymized.

The conditions for the termination of the experiment were described in chap. 5.4.

There is no disadvantage for the participants if they discontinue their participation in the study.

SUPSI

8 STUDY INTERVENTION

8.1 Medical Device ID

8.1.1 Intervention product

The intervention products are topical ointments/creams/gels available without a prescription with a warming or cooling effect. The warming products are based on wintergreen oil, the cooling products on menthol and/or alcohol base. Eight different products are included. Of these, three products are said to have a warming effect (Axanova hot gel, Perskindol Dolo Gel, Dolor-X Hot Gel), three products to have a cooling effect and then a warming effect (Axanova activ gel, Perskindol Classic Gel, Dolor-X Classic Gel) and two products to have a cooling effect (Perskindol Cool Cooling Gel, Dolor-X Cool Gel).

In the context of the sub-analysis, the product Axanova hot gel serves as an intervention product.

Securing the test subjects

Only subjects who have completed the health questionnaire without risk factors, successfully passed the product testing without skin intolerance and the screening with regard to skin discrimination will be admitted to the study. In this way, at-risk test subjects are detected at an early stage and are not recruited for the study.

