--	---

SUPSI

Study Product / Intervention:	Over-the-counter, topical ointments/creams/gels with a warming or cooling effect
Control Intervention (if applicable):	The mutual paravertebral area of the lumbar back, which does not receive any application, acts as a control.
Number of Participants with Rationale:	
We limit the number of subjects to N = 45 per warming or cooling product. A total of N = 90 subjects will be recruited.
 
As part of a planned sub-analysis, an additional N = 15 subjects will be recruited. Thus, the total number of subjects increases to N = 105.
 
Previous studies on topical diclofenac applications have tested groups of up to 200 subjects^{4,6,7}. Roth et al. 2004 limited themselves to N = 80 subjects¹². Lasanen et al. 2016 tested N = 10 subjects, they used a gel without drug ingredients⁸.

Study Duration:	March 2017-December 2020
Study Schedule:	
March 2017: effective start of measurements
 
December 2020: planned end of measurements

Investigator(s):	
Examiner
 
 - [name]^{1,2} - [name]^{1,2} - [name], Drs, MSc^{1,2} - [name], MSc² 
<small>1University College Physiotherapy "Thim van der Laan", [name] 2University of Applied Sciences and Arts Southern Switzerland, Department of Business Economics, Health and Social Care, Physiotherapy Graubünden, [name]</small>
 
Contact / Director of Studies [name], PhD University of Applied Sciences and Arts Southern Switzerland Department of Business Economics, Health and Social Care Physiotherapy Graubünden [name] [contact] [contact]

SUPSI

Study Centre(s):	
Single Centre Study:
 
University of Applied Sciences and Arts Southern Switzerland Physiotherapy Graubünden [name]

Statistical Considerations:	
Local changes in skin characteristics during and after a topical application of a warming or cooling product - a randomized, controlled, clinical trial.
 
Repeated measures analysis of variance (MANOVA)
 
2 factors:
 
 - Topical application (warming versus control / cooling versus control) - Time (baseline, time 0min, 10min, 20min, 30min, 40min, 50min, 60min post-application) 
The significance level is set at $P < 0.05$, and the statistical data analysis is carried out with SPSS V. 23.

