The aim of our study is to investigate local changes in skin characteristics during and after a topical application of an over-the-counter, warming or cooling product without medicinal ingredients using non-invasive methods. Products with arnica or wallwort are excluded so as not to influence the subjective sensation of the subject. Products containing menthol, alcohol derivatives and wintergreen oil are included. The objective parameters are the perfusion of the microcirculation of the skin, erythema formation, skin surface temperature, oxygen saturation of the superficial muscles and the subjective temperature perception of the subject. The parameters are collected as a baseline before the application of the product, then directly in the postal application at 0 min, then in 10-minute intervals up to one hour of postal application. Thus, 8 measurement moments take place. The aim is to record the local changes in skin characteristics during and after a topical application and to recognize the effects of the products. The current state of scientific knowledge requires further studies with topical products without medicinal ingredients in order to substantiate or refute the effects already established.

Our preliminary study results of the effects of the warming products showed that one of the three tested products led to more significant changes in the measured skin parameters compared to the remaining two products. However, none of the three products had an effect on deeper tissue. However, this aspect is of great importance within rehabilitation and physiotherapy with regard to wound healing, regeneration and muscle tone. In the meantime, we have two more sensitive measuring instruments at our disposal, which can record the perfusion of the skin microcirculation up to the capillary bed and the oxygen saturation of the tissue up to a maximum depth of 30 mm. As part of a sub-analysis, we therefore plan to recruit additional N = 15 subjects to repeat the measurements with these more sensitive measuring instruments. The warming product with the greatest effect (shown above) serves as an intervention product.

Abbreviations

SUPSI

CEC	Competent Ethics Committee
GCP	Good Clinical Practice
Ho	Zero hypothesis
H1	Alternative hypothesis
KlinV	Ordinance on Clinical Trials in Human Research

SUPSI

Study Schedule

The completion of the measurement series is planned for October 2019, and the completion of the entire project for December 2020.

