3.6 Peers

Topical application versus no application

The test subject receives the product to be applied paravertebrally on one side, while the other side acts as a control. All test subjects are measured under the same environmental factors, the products to be applied are applied in the same way, quantity and technique.

Randomization

Randomization takes place with regard to the application side and the product to be applied. The application is paravertebral one-sided, the opposite side acts as a control. The allocation is made by drawing a lot.

The data obtained in this way is pooled accordingly after the application.

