11.4.2 Primary Analysis

The statistical data analysis will be carried out by [name] after completion of the data collection of the entire project.

Repeated measures analysis of variance (MANOVA)

2 factors:

Factor 1: Intervention (warming product versus control / cooling product versus control)

Factor 2: Time (baseline, 0min, 10min, 20min, 30min, 40min, 50min, 60min postal application)

The significance level is set at $P < 0.05$, and the statistical data analysis is carried out with SPSS V. 23.

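### Eight products of three stated effect types are analysed as two classes, with no rule placing the three cooling-then-warming products and no prespecified product-level analysis

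*Combined protocol and SAP*

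**What the plan says.** Section 8.1.1 states "Eight different products are included" and sorts them by claimed action. One group of three is purely warming and a pair is purely cooling. The group at issue here is listed as "three products to have a cooling effect and then a warming effect (Axanova activ gel, Perskindol Classic Gel, Dolor-X Classic Gel".

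The inferential plan is coarser. Section 11.1 has hypotheses for a warming product and for a cooling product only. Section 11.4.2 gives "Factor 1: Intervention (warming product versus control / cooling product versus control", crossed with an eight-level time factor. Section 11.4.3 plans no secondary analysis. Nothing assigns the cooling-then-warming products to a class.

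On allocation, section 3.6 says "Randomization takes place with regard to the application side and the product to be applied", and 7.3 puts both product and side on the lot. Section 6.1.1 describes randomisation to a warming or a cooling group, plus side. Table 1 schedules warming-product data collection in 2017 and cooling-product collection in 2019.

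The overview (Aim of the study) reports that "one of the three tested products led to more significant changes in the measured skin parameters compared to the remaining two products" and uses this to choose the product for a further 15 subjects. The synopsis says "We limit the number of subjects to N = 45 per warming or cooling product", with 90 in total before those 15.

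**The concern.** The study aims to identify what the products do. Three of the eight are described as reversing direction during follow-up, and the plan gives them no place.

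- If they sit in the cooling class, their later warming opposes the two cooling products at the same time points.
- If they sit in the warming class, their early cooling opposes the warming products.
- If they sit in neither, no planned analysis covers them.

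In the first two cases the class mean at some time points describes none of its products, and product differences go into the error term. A cooling class could then look inert, or even warming, late in the hour. In every case product comparisons are left to be chosen after the data are seen, although product is recorded for each subject at allocation.

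**Working it through.** **1. The plan's own figures.** 3 + 3 + 2 = 8 products. 45 × 2 = 90, and 90 + 15 = 105, as the synopsis states. Forty-five for each of eight products would be 8 × 45 = 360, so the synopsis figure can only mean 45 per class. Section 11.2 justifies the total by feasibility and gives no effect size, SD or power, so there is no power calculation to reproduce.

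**2. Number per product, by placement.** The documents give neither the placement nor the allocation ratio. Equal allocation within class is assumed.

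| Placement of the three cooling-then-warming products | Per product, warming class | Per product, cooling class |
|---|---|---|
| Cooling class | 45/3 = 15 | 45/5 = 9 |
| Neither class | 45/3 = 15 | 45/2 = 22.5 |
| Warming class | 45/6 = 7.5 | 45/2 = 22.5 |

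The overview refers to three tested warming products, which matches the three purely warming products in 8.1.1. That makes the third row the least likely, but this is an inference.

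**3. Class mean at one late time point, cooling-class placement.** There are 2 × 9 = 18 subjects on cooling products and 3 × 9 = 27 on cooling-then-warming products. Assume a late effect of -1 for the former and +b for the latter:

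class mean = (18 × (-1) + 27 × b) / 45

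- b = 0: -18/45 = -0.4
- b = 0.5: (-18 + 13.5)/45 = -0.1
- b = 1: (-18 + 27)/45 = +0.2

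For power, assume late effects of -0.8 and +0.8 SD of the treated-minus-control difference. The class mean is 0.8 × (27 - 18)/45 = 0.16. The pooled variance is 1 + 0.64 - 0.0256 = 1.6144, so the standardised mean is 0.16/1.271 = 0.126. A paired two-sided 5% t-test at n = 45 then has about 13% power. Analysed by type, power is 98% (n = 27) and 89% (n = 18).

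**4. The other placements.** In the warming class (22.5 against 22.5), equal and opposite early effects average to zero. In neither class, nothing cancels, but nothing is planned for these products.

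**5. What the per-product numbers can detect.** For a paired t-test at a single time point (two-sided 5%, 80% power, noncentral t), the detectable treated-minus-control difference is 0.43 SD at n = 45, 0.78 SD at n = 15 and 1.07 SD at n = 9. Comparing two products with each other (two-sample t-test) needs 1.06 SD at 15 each and 1.41 SD at 9 each. These are single-time-point benchmarks, not the power of the planned repeated-measures model.

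**The case against.** Several points on the other side are sound.

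- **The model.** Factor 1 is treated versus untreated side, taken separately for warming and cooling, so warming and cooling products are not averaged together. The eight-level time factor also keeps a cool-then-warm course visible within a product. This stands: any cancellation is between products at the same time point.
- **Opposite effects are averaged.** A reader might infer this as fact. The documents never say that the cooling-then-warming products are pooled with the cooling ones. Sections 3.6 and 7.3 pool data by application, which could mean by product, and factor 1 is worded in the singular. The directions are only what the products are said to do. Pooling is therefore a risk that the plan leaves open. The ambiguity is no defence, because 11.4.2 contains no product term.
- **The product is never analysed.** A reader might infer this too. The overview reports a comparison among the three warming products, and the 15 additional subjects receive one named product, Axanova hot gel. What can be said is that product-level analysis is not prespecified, and that one such comparison, with no stated multiplicity control, already steered a later choice.
- **The preliminary result.** It shows a difference in degree among warming products, not in sign. It supports reporting products separately; it does not make an average warming effect meaningless.
- **Randomisation.** It is not settled that product is what is randomised. Sections 3.6 and 7.3 say so, 6.1.1 names only the class, and Table 1 separates the two classes by two years, so on that schedule product could be randomised only within a phase.

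**Conclusion.** The point holds as a gap in the plan. Three of eight products belong to an effect type with no hypothesis and no assigned class, and no product or effect-type term is prespecified, although product is noted on the lot. Followed as written, the plan either mixes these products with others said to act in the opposite direction or omits them.

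The size depends on the unstated placement. Under equal allocation, all five products in one class of 45 and the assumed effects, a late cooling effect of -1 becomes -0.4 to +0.2. With only the two cooling products in the class, it is not diluted at all. The per-product numbers of 15, 9 and 22.5 are likewise consequences of assumed allocation and placement; a reader should not take them as the trial's actual group sizes. That 45 is a per-class figure follows from the total of 90 and needs no assumption.

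**What to change.** 1. In 11.1 and 11.4.2, assign each of the eight products to one of the three effect types in 8.1.1, and analyse the types separately.
2. Within type, add product as a between-subject factor with its interactions with side and time. Report treated-minus-control curves per product.
3. Do not report a pooled cooling or warming effect that contains the cooling-then-warming products.
4. Label the product comparison for the completed warming phase as post hoc. For the cooling phase, prespecify it with a stated multiplicity approach.
5. Correct the synopsis to 45 per class and state the planned number per product. Under equal allocation this is 15 per warming product and 9 to 22.5 per product in the cooling class, depending on placement. Give the corresponding detectable differences.
6. Reconcile 3.6 and 7.3 with 6.1.1 and Table 1 on whether product or only class is randomised.

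The cost is protocol and SAP wording and one more model factor. No extra measurements are needed, since the product is already on each lot. The price is less precise per-product estimates, less favourable stated sizes, and more comparisons: within types there are 3 + 3 + 1 = 7 product pairs for each outcome.
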